5.1.3. Inclusion Criteria Specific for IgAN Cohort

- Established diagnosis of primary IgAN based on kidney biopsy (Section 10.9) obtained any time prior to or during the Screening Period.
- 13. Mean proteinuria ≥ 1 g/day on 2 complete and valid 24-hour urine collections during the Screening Period.
- 14. For participants with a kidney biopsy performed > 1 year prior to Screening that was used for eligibility:
 - Presence of hematuria as defined by a positive result for blood on urine dipstick or ≥ 10 red blood cells (RBCs)/high-power field (hpf) microscopy on urine sediment (documented by the local laboratory) during Screening Period. Presence of hematuria documented by the central laboratory may also be acceptable.
- 15. Compliance with stable and optimal dose of RAS inhibitor treatment including maximum allowed or tolerated ACE inhibitor and/or ARB dose for ≥ 3 months prior to Screening with no expected change in dose during the Blinded Treatment Periods (through Week 50) (participants with established intolerance to RAS inhibitors may be included).
- Controlled and stable blood pressure (defined as < 140/90 mmHg) over the past 3 months prior to randomization.

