- 14. History of hypersensitivity to any ingredient contained in the study intervention, including inability to take or tolerate the allowed concomitant therapies consistent with the standard of care (Section 6.5.3), with the exception of RAS inhibitors for the IgAN cohort (inclusion criterion 15).
- 15. History of malignancy within 5 years prior to Screening with the exception of nonmelanoma skin cancer or carcinoma in situ of the cervix that has been treated with no evidence of recurrence
- 16. Evidence of hepatitis B (positive hepatitis surface antigen [HBsAg] or positive core antibody (anti-HBc) with negative surface antibody [anti-HBs]) or hepatitis C viral infection (hepatitis C virus [HCV] antibody positive, except for patients with documented successful treatment and documented sustained virologic response [SVR]) at Screening
- Evidence of human immunodeficiency virus (HIV antibody positive) infection at Screening

- 18. Bone marrow insufficiency with absolute neutrophil count $< 1.3 \times 10^3 / \mu L$; thrombocytopenia (platelet count $< 50,000/mm^3$)
- Active systemic bacterial, viral, or fungal infection within 14 days prior to first dose of study intervention
- Presence of fever as documented by a temperature ≥ 38°C (100.4°F) within 7 days prior to administration of study intervention on Day 1
- 21. History of Neisseria meningitidis infection

Prior/Concomitant Therapy

- 22. Current treatment with a biologic medication that may affect immune system functioning, or has stopped treatment with a biologic medication that may affect immune system functioning, and 5 terminal half-lives of the biologic medication have not elapsed by the time of the Screening Visit, or treatment with belimumab or rituximab ≤ 6 months prior to Screening
- Any previous or current treatment with complement inhibitors (eg, eculizumab, ravulizumab)
- 24. Use of known cytochrome P450, family 3, subfamily A (CYP3A) sensitive substrates, moderate or strong CYP3A inducers, and/or moderate or strong CYP3A inhibitors from 2 weeks or 5 half-lives, whichever is longer, prior to the first administration of study intervention on Day 1 (randomization). The full list provided in Section 10.16)
- 25. Use of selected medications known to lower the seizure threshold and/or cause seizure. See Section 10.15 for list of medications

Prior/Concurrent Clinical Study Experience

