5.2.2. Exclusion Criteria Specific for LN Cohort

- 28. Participants who have initiated any of the following treatments for the current active LN flare:
 - a. Cyclophosphamide ≤ 6 months prior to Screening
 - b. CNIs ≤ 1 month prior to Screening
 - A cumulative dose of intravenous (IV) methylprednisolone > 3 g
 - d. Mycophenolate mofetil > 2 g/day (or equivalent) for ≥ 8 consecutive weeks prior to Screening
 - e. Prednisone or prednisone equivalent ≥ 0.5 mg/kg/day for ≥ 8 consecutive weeks prior to Screening
- Uncontrolled hypertension (systolic blood pressure > 160 mmHg or diastolic blood pressure > 110 mmHg) on 2 or more measurements during the Screening Period

- Prior history or clinically active SLE related cerebritis, seizures, stroke, or stroke syndrome requiring treatment or clinically active pericarditis
- Inability to take or tolerate the allowed concomitant therapies consistent with the standard of care.

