9.3. Populations for Analyses

The population sets used for analysis are defined below.

Analysis Set	Description		
Enrolled Set	All consented participants excluding screen failures.		
Randomized Set	All randomized participants. Participants will be analyzed as randomized for reporting disposition, demographics, and baseline characteristics.		
Full Analysis Set (FAS)	All randomized participants who receive at least 1 dose of study intervention. Participants will be analyzed as randomized for reporting efficacy data.		
Safety Set	All participants who receive at least 1 dose of study intervention. Participants will be analyzed according to the study intervention they actually received for reporting exposure and safety data.		
Per Protocol Set	All randomized participants who receive at least 1 dose of study intervention and without important protocol deviations.		
Pharmacokinetic (PK) Analysis Set	All randomized participants who receive at least 1 dose of study intervention and who have a baseline PK value and at least 1 evaluable postdose PK assessment.		
Pharmacodynamic (PD) Analysis Set	All randomized participants who receive at least 1 dose of study intervention and who have a baseline PD value and at least 1 evaluable postdose PD assessment.		

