3. ANALYSIS SETS

The participant analysis sets are defined as follows in Table 2:

 Table 2:
 Participant Analysis Sets

Participant Analysis Set	Description			
Randomized Set	The Randomized Set includes all randomized participants. Participants will be analyzed as randomized for reporting disposition, demographics, and baseline characteristics.			
Full Analysis Set (FAS)	Participants who have been randomized and received at least 1 dose of study intervention will be included in the FAS. Participants in FAS will be analyzed as randomized for reporting efficacy data.			
Modified Full Analysis Set (mFAS)	All FAS participants excluding participants who were impacted by coronavirus disease 2019 (COVID-19) as follows: 1. Participants who missed > 20% of total ALXN2050 dose amount assigned per protocol after the scheduled dosing time point during the 26-week Blinded Initial Evaluation Period due to COVID-19 2. Participants who withdrew early from the study during the 26-week Blinded Initial Evaluation Period due to COVID-19. 3. Participants who received concomitant treatments for COVID-19 during the 26-week Blinded Initial Evaluation Period that could potentially affect efficacy 4. Participants who were hospitalized due to a COVID-19 related adverse event during the 26-week Blinded Initial Evaluation Period Inclusion in the mFAS will be determined for each participant prior to			
Per-Protocol Set (PPS)	database lock. Participants to be included in the PPS need to meet all the following criteria: • For the LN cohort, satisfy the following specific inclusion criteria (IC)/exclusion criteria (EC): ○ IC No. 9: Active focal or diffuse proliferative LN Class or IV confirmed by biopsy obtained ≤ 6 months prior to Screening or during Screening Period ○ IC No. 10: Clinically active LN at Screening requiring/receiving immunosuppression induction treatment ○ IC No. 11: Proteinuria with UPCR ≥ 1 g/g based on one 24-hour urine collection ○ EC No. 28: Received any of the specified treatments defined in Protocol Section 5.2.2 ○ EC No. 29: Uncontrolled hypertension (systolic blood pressure > 160 mmHg or diastolic blood pressure > 110 mmHg) on 2 or more measurements			

 Table 2:
 Participant Analysis Sets

Participant Analysis Set	Description			

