	 EC No. 30: Prior history or clinically active SLE-related cerebritis, seizures, pericarditis, stroke, or stroke syndrome requiring treatment For the IgAN cohort, satisfy the following specific inclusion criteria (IC) or exclusion criteria (EC): IC No. 12: Established diagnosis of primary IgAN based on kidney biopsy 			
	 IC No. 13: Mean proteinuria ≥ 1 g/day on 2 complete and valid 24-hour urine collections 			
	 IC No. 15: Compliance with stable and optimal dose of RAS inhibitor treatment 			
	 IC No. 16: Controlled and stable blood pressure (defined as < 140/90 mmHg) 			
	 EC No. 35: Prednisone or prednisone equivalent > 20 mg/day for > 14 consecutive days or any other systemic immunosuppression within 6 months prior to Screening 			
	o EC No. 37: Body mass index ≥ 38 kg/m² during Screening			
	 For both cohorts, satisfy the following criteria: 			
	 Participants who have an eGFR > 30 mL/min/1.73 m² during Screening 			
	 Participant informed consent/assent was provided prior to study procedures being carried out 			
	 Received correct treatment per randomization schedule Remained blinded to treatment allocation during the 26-week Blinded Initial Evaluation Period 			
	 Received > 80% of planned dose of study intervention during the 26-week Blinded Initial Evaluation Period 			
	 Received appropriate allowed concomitant therapy during the 26-week Blinded Initial Evaluation Period 			
	 Received appropriate additional standard of care therapy, if required by protocol, during the 26-week Blinded Initial Evaluation Period (LN cohort only) 			
	 Did not receive any disallowed medications or therapies considered having significant impact on the primary efficacy measure during the 26-week Blinded Initial Evaluation Period (defined in Protocol Section 6.5.2) 			
	The PPS will be determined prior to database lock.			
Safety Set (SS)	All participants who received at least 1 dose of study intervention will be included in the SS. Participants will be analyzed according to the study intervention they actually received for reporting exposure and safety data.			
	The SS is the primary analysis for all safety and exposure analyses.			

 Table 2:
 Participant Analysis Sets

Participant Analysis Set	Description
Pharmacokinetic (PK) Analysis Set	All randomized participants who received at least 1 dose of study intervention and who have a baseline PK value and at least 1 evaluable postdose PK assessment will be included in PK Analysis Set.

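### The SAP's Per-Protocol Set restates exclusion criteria 30 and 35 more broadly than the protocol, so applied as written it removes eligible participants

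*SAP*

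**What the plan says.** Protocol Section 9.3 defines the PPS in general terms: "All randomized participants who receive at least 1 dose of study intervention and without important protocol deviations". SAP Section 3, Table 2, replaces this with a list: "Participants to be included in the PPS need to meet all the following criteria". The list names selected inclusion and exclusion criteria by protocol number, each with a short text, and adds conduct items such as dose received, blinding and disallowed medication during the first 26 weeks. It does not repeat the condition about important deviations.

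Two entries matter here.

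- **Criterion 30 (LN).** SAP: "EC No. 30: Prior history or clinically active SLE-related cerebritis, seizures, pericarditis, stroke, or stroke syndrome requiring treatment". Protocol Section 5.2.2: "Prior history or clinically active SLE related cerebritis, seizures, stroke, or stroke syndrome requiring treatment or clinically active pericarditis".
- **Criterion 35 (IgAN).** After the prednisone threshold, the SAP continues with "any other systemic immunosuppression within 6 months prior to Screening". Protocol Section 5.2.3 has the same threshold and the same six-month window, but adds that the treatment was for IgAN.

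The PPS is used twice. Protocol Section 9.4.6.1 and SAP Section 4.2.4 repeat the primary endpoint analysis on it, and SAP Section 4.2.3 repeats the dosing-pause sensitivity analysis on it. SAP Section 4.8, on changes from the protocol's planned analyses, mentions only the handling of hematuria.

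**The concern.** A per-protocol analysis asks whether the result holds among participants who were enrolled and treated as the protocol requires. If its entry rule is stricter than the protocol, it removes people who complied, and a difference from the FAS result may then reflect the altered rule rather than non-compliance.

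The main comparison is small: 30 + 30 = 60 planned LN participants and 24 + 24 = 48 planned IgAN participants on 180 mg or placebo. One participant is 1/60 = 1.7% or 1/48 = 2.1% of that comparison. Membership is fixed before database lock, and a correction made later could be taken for selection after seeing results.

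**Working it through.** The plan states no figure on this point, so the check is a comparison of texts.

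**1. Criterion 30.** In the protocol, the phrase about prior history or current activity governs cerebritis, seizures, stroke and stroke syndrome. Pericarditis stands apart at the end with its own condition, clinical activity. The SAP moves it into the first group.

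| LN participant | Protocol criterion 30 | SAP PPS text |
|---|---|---|
| Clinically active pericarditis | excluded | fails |
| Past SLE-related pericarditis, resolved | eligible | fails |

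The closing words about requiring treatment may narrow the second row to episodes that were treated. They do not remove it.

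**2. Criterion 35.** The SAP keeps dose, duration and time window but not the indication.

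| IgAN participant | Protocol criterion 35 | SAP PPS text |
|---|---|---|
| Systemic immunosuppression for IgAN in the 6 months before Screening | excluded | fails |
| The same for another indication, stopped before entry | not excluded by this criterion | fails |

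The second row is narrow. Immunosuppression that continues on study is prohibited for IgAN by Protocol Section 6.5.2 and could fail the PPS for that reason.

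**3. Can the broader texts be applied?** Yes. Protocol Section 8.12.4 collects medical history. Section 8.2.5 collects systemic immunosuppression within 2 years of the Screening Period, with the reason for use. If PPS membership is derived from those data using the SAP text, the second rows take effect. If it is derived only from recorded failures of protocol criteria, they do not. The SAP does not say which source is used.

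**4. The closed list against Protocol Section 9.3.** Exclusion 22 covers, among other things, "treatment with belimumab or rituximab ≤ 6 months prior to Screening". Exclusion 23 covers any previous or current complement inhibitor. Neither is in the PPS list. Criterion 28, which is listed for LN, names cyclophosphamide, CNIs, IV methylprednisolone, MMF and prednisone, but no biologic or complement inhibitor. The disallowed-medication item covers only the 26 weeks on study. By the list alone:

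- an LN participant randomized in breach of exclusion 22 for prior biologic use stays in the PPS;
- a participant in either cohort randomized despite past complement-inhibitor use stays in;
- an IgAN participant with recent rituximab or belimumab would probably be removed by the SAP's broad criterion 35, if these count as systemic immunosuppression. Once criterion 35 is corrected, that incidental protection goes for a non-IgAN indication.

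**5. Size.** The documents give no frequency for past pericarditis, for immunosuppression given for other indications, or for enrollment in error. Neither the number moved nor the effect on the PPS estimate can be computed.

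**The case against.** The strongest reply is that Table 2 cites criteria by number and the accompanying text is only a label. Several labels are plainly shortened: criterion 10 loses the reference to the Investigator's opinion, criteria 11 and 29 lose the Screening Period, criterion 16 loses the three-month window, and criterion 28 merely points to the protocol. On that view the numbered criterion governs and nothing has changed.

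This stands for criterion 15. The SAP has "IC No. 15: Compliance with stable and optimal dose of RAS inhibitor treatment", and a reader might infer that RAS-intolerant participants are removed. The documents do not support that. The protocol's exception, "participants with established intolerance to RAS inhibitors may be included", is part of criterion 15 itself, so an intolerant participant satisfies the criterion that the SAP cites.

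It is weaker for the two entries at issue. In criterion 30 a term has been moved, not left out, and shortening does not explain that. In criterion 35 the label gives dose, duration and window in full and omits only the indication, so it reads as the complete rule.

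A second reply is that choosing which criteria count is the SAP's job. Protocol Section 9.4 leaves detail to the SAP, and many other criteria are unlisted. That is fair: omitting exclusions 22 and 23 is selection, not restatement. Protocol Section 5 permits no waivers, so it matters only for someone randomized in error. What remains is that the list is not reconciled with Protocol Section 9.3.

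A third reply is that errors would be visible, because SAP Section 6.2.1 summarizes participants who fail eligibility criteria. That helps with breaches. It does not help with a compliant participant dropped by the SAP text, who has failed no protocol criterion and would show up only in the listing of analysis populations.

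**Conclusion.** The point holds for criteria 30 and 35: the SAP text differs in substance from the protocol, the difference is undeclared, and applied literally it removes participants who met the protocol from one supplementary and one repeated sensitivity analysis. This rests on the SAP text, not just the criterion number, being used to set membership.

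The impact is limited. The primary analysis is on the FAS, no decision rule depends on the PPS, and the number affected is unknown. Any count would rest on frequencies that the documents do not contain.

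A reader might go further and infer that the PPS keeps recent rituximab or belimumab users in both cohorts. For IgAN the documents do not support this, because the SAP's own broad criterion 35 would probably remove them. For LN it applies only to a participant randomized in breach of exclusion 22, and only if the important-deviation condition in Protocol Section 9.3 is taken as superseded.

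**What to change.** In SAP Table 2, replace the restated texts for criteria 30 and 35 with a reference of the form: met protocol criterion No. X as worded in Protocol Section 5. Using the same form for the other listed criteria also settles any doubt about the RAS-intolerance exception in criterion 15.

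In the same edit, reconcile the list with Protocol Section 9.3. Either restore the condition that there be no important protocol deviation, or add exclusions 22 and 23, or state why they are left out. This should accompany the correction of criterion 35, because that correction otherwise opens the exclusion 22 gap in IgAN. Record any remaining difference from the protocol definition in SAP Section 4.8.

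The cost is SAP wording before PPS membership is fixed at database lock. No new data are needed: eligibility failures, medical history and prior immunosuppression are already collected.

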Physical examination, including neurological assessments ^f	х	X							Х		Section 8.2.1.	
Abbreviated PE			X	X	X	X	X	X				
Vital signs	X	X	X	X	X	X	X	X	X	X	Vital signs to be taken predose at clinic visits (Section 8.2.2).	
ECG for LN patients on hydroxychloroquine	Х	Х	Х	X	X	X	Х	Х	Х	X	Section 8.2.3.	
ECG for LN patients not on hydroxychloroquine	X	Х							X			
Prior medications and procedures	Х										Section 8.2.5.	
Concomitant medications and NPTP			Continuous monitoring							X	Section 6.5 and Section 8.2.5.	
Allowed concomitant LN therapy		Continuous monitoring								X	See details on corticosteroid taper in Section 6.5.3.1.	
Adverse events			Continuous monitoring								Section 10.3.	

Table 1: Schedule of Activities During Screening and the Blinded Initial Evaluation Period: Screening to Week 26 Visit (LN Cohort)

Period	Screen- ing			Initi	al Evalu	ation Pe		Notes			
Visit	1	2	3	4	5	6	7	8	9	Evaluation for Renal	Unscheduled visits can be performed
Week	Up to 6 W		W2	W4	W8	W12	W16	W20	W26/ ED ^b	Flare and Extrarenal	as needed. An ED Visit is required if participant discontinues study early.
Days and Window	D -42 to -1	D1	D15 ±3	D29 ± 3	D57 ± 5	D85 ± 5	D113 ±5	D141 ±5	D183 ± 5	SLE Flare Assessment Visit ²	
Predose blood sample for clinical chemistry, hematology, and coagulation	Х	X	X	X	X	X	X	X	X	x	Section 8.2.4.2 and Section 10.2.
Urinalysis and urine sediment	X	X	X	X	X	X	X	X	X	X	Section 8.2.4.3 and Section 10.2.
Participant safety card review		X	X	X	X	X	X	X	X	X	Confirm participants carry safety card at all times (Section 8.2.7).
PK and PD Assessments ⁸											
Predose blood sample for PK		X	X	X	X	X	X		X	X	
Predose blood sample for Bb and AP activity		X	X	X	X	х	X		X	x	See footnote for sampling timepoints.
Postdose blood sample for PK		X	X								
Postdose blood sample for Bb and AP activity		х	х								
Exploratory Assessments											
EQ-5D-5L		X			X		X		X		If possible, complete the PROs prior to
SF-36		X			X		X		X		procedures and intervention administration (Section 8.10).
FACIT-Fatigue		X			X		X		X		
SLEDAI-2K		X							X	x	Required at Day 1 and Week 26/ED; perform as needed for evaluation of Extrarenal SLE Flare (Section 8.1.7).
Blood and urine samples for biomarkers	Х	X	X		X		X		X	X	Collect predose on in-clinic dosing days (Section 10.2).

Table 1: Schedule of Activities During Screening and the Blinded Initial Evaluation Period: Screening to Week 26
Visit (LN Cohort)

Period	Screen- ing			Initi	ial Evalu	ation Pe	riod		Notes		

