b For participants who discontinue study intervention prior to Week 50, every effort should be made to have the participant continue the study visits as per the SoA through the Week 50. A Safety Follow-up Visit should be performed 30 days after the last dose of study intervention. If the participant does not agree to continue with the study visits after study intervention is discontinued, the ED Visit should be performed as soon as possible, and a Safety Follow-up Visit should be performed 30 days after the last dose of study intervention (refer to Table 5 for the Safety Follow-up Visit procedures.

Table 1: Schedule of Activities During Screening and the Blinded Initial Evaluation Period: Screening to Week 26 Visit (LN Cohort)

- ^c To reduce the risk of meningococcal infection (*Neisseria meningitidis*), all participants must be vaccinated against meningococcal infection within 3 years or before the administration of study intervention on Day 1. Participants who initiate study intervention less than 2 weeks after receiving a meningococcal vaccine must receive treatment with appropriate prophylactic antibiotics until at least 2 weeks after vaccination (Section 6.5.5).
- ^d FSH test need not be done if documentation confirming postmenopausal status is available (Section 8.2.4.4).
- Renal Flare requires a 24-hour urine collection for confirmation (Section 8.1.1).
- f Perform a symptom based neurologic examination if participant has complaints or clinical findings attributable to the CNS and if positive for findings, full neurologic examination to be performed at each assessment timepoint.
- Fredose: collect within 0.5 h predose on indicated in-clinic dosing days. Postdose: approximately 50% participant in each treatment arm will be assigned to PK/PD sample collection at 2 ± 0.5 h, 4 ± 0.5 h, and 6 ± 0.5 h postdose on Day 1 and at 2 ± 0.5 h, 4 ± 0.5 h, 6 ± 0.5 h postdose at Week 2. For the other approximate 50% of participant, samples will be collected at 2 ± 0.5 h postdose on Day 1 and 2 ± 0.5 h postdose at Week 2 (Section 8.4 and Section 8.5)
- Participants may receive a kidney biopsy for clinical reasons or for evaluation of a Renal Flare (as defined in Section 8.1.6) at the discretion of the Investigator. The local pathology report and microsection slides from kidney biopsies performed at other times during the study prior to Week 26 should also be sent to the Central Pathology Laboratory for review as soon as possible.

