Pharmacodynamic (PD) Analysis Set	All randomized participants who received at least 1 dose of study intervention and who have a baseline PD value and at least 1 evaluable postdose PD assessment will be included in PD Analysis Set.

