4.6.2. PK/PD Analysis (Both Cohorts)

The SS will be used for PK concentration listings and individual figures, and the PK Analysis Set will be used for PK parameter listings, summary tables, and mean figures.

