6.1.2. Definition of Baseline Values

For the 26-week Blinded Initial Evaluation Period, baseline is defined as the last available assessment value prior to the first dose of study intervention. For the 24-week Blinded Extended Treatment Period, a re-baseline is defined as the last available assessment prior to the first dose of study intervention administered in the extension period.

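### The PK Analysis Set requires a Day 1 baseline concentration that no planned PK summary uses, so one missed draw removes a participant from the PK summary tables, mean figures and parameter listings

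*SAP*

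**What the plan says.** SAP Section 3 (Table 2) restricts the PK Analysis Set to dosed, randomized participants "who have a baseline PK value and at least 1 evaluable postdose PK assessment will be included in PK Analysis Set". Protocol 9.3 agrees: "who have a baseline PK value and at least 1 evaluable postdose PK assessment". The PD Analysis Set carries the parallel condition, "who have a baseline PD value and at least 1 evaluable postdose PD assessment will be included in PD Analysis Set".

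SAP 6.1.2 fixes the term for the first period: "baseline is defined as the last available assessment value prior to the first dose of study intervention". It also defines a re-baseline before the first extension-period dose. SAP 4.1.4 does not impute missing baselines.

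In the Schedule of Activities (Protocol 1.3, Tables 1 and 2), the row "Predose blood sample for PK" is empty at Screening and first marked on Day 1, with the instruction "collect within 0.5 h predose on indicated in-clinic dosing days". SAP 4.6.2.1 counts results below the limit of quantification (BLQ) as zero in descriptive statistics.

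SAP 4.6.2 divides the outputs. Concentration listings and individual figures use the Safety Set, while "the PK Analysis Set will be used for PK parameter listings, summary tables, and mean figures".

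**The concern.** A membership rule should ask for the data that the analysis needs. The PK endpoint (Protocol Section 3) is observed concentration over time. The planned summaries are concentrations by day and time point (SAP 4.6.2.1), PK parameters (SAP 4.6.2.2), and trough and peak concentrations (Protocol 9.4.8). None is a change from baseline. The Day 1 predose value supplies its own row in the table and enters no other planned PK summary.

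It also carries no exposure information. ALXN2050 is a complement factor D inhibitor (Protocol 2.2.2), exclusion criterion 23 bars anyone who has ever had a complement inhibitor (Protocol 5.2.1), and the sample precedes the first dose. Nor does the rule work as a quality check, because it asks only that a value exist. A participant with unexpected measurable drug before dosing stays in, while one with a lost tube and valid later samples goes out.

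At stake is the completeness of the descriptive PK outputs, which are thinnest in the 120 mg arms. Protocol 4.2 (Table 9) includes those arms to give supportive, descriptively summarized data.

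**Working it through.** The plan states no figure for the size of the PK Analysis Set, so there is nothing to reproduce. The check traces the rule to its effect, counts the scheduled draws affected, and sizes one exclusion.

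**Chain from missed draw to exclusion**
- Membership needs a baseline PK value (SAP Section 3, Protocol 9.3).
- Baseline is the last value before first dose (SAP 6.1.2), and Day 1 predose is the only PK draw before first dose (Protocol Tables 1 and 2).
- Missing baselines are not imputed (SAP 4.1.4).
- So a participant without a usable Day 1 predose sample is out of the set, whatever the later samples show.

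**Scheduled concentrations after the first dose (Protocol Tables 1 to 4)**
- LN predose: Weeks 2, 4, 8, 12, 16, 26, 34, 42 and 50 = 9.
- IgAN predose: Weeks 2, 6, 12, 18, 26, 28, 32, 38, 42 and 50 = 10.
- Postdose on Day 1 and Week 2: about half of each arm at 2 h only (2 samples), the rest at 2, 4 and 6 h (6 samples).
- Total through Week 50: LN 9 + 2 = 11 or 9 + 6 = 15; IgAN 10 + 2 = 12 or 10 + 6 = 16.
- Total through Week 26: LN 6 + 2 = 8 or 6 + 6 = 12; IgAN 5 + 2 = 7 or 5 + 6 = 11.

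Unscheduled LN flare visits would add to these and are not counted. The totals describe participants randomized to ALXN2050. An IgAN placebo participant who switches at Week 26 has 5 scheduled concentrations after the first ALXN2050 dose through Week 50 (Weeks 28, 32, 38, 42 and 50).

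**Cost of exclusions**

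Planned arm sizes are from Protocol 4.1.2 (Table 8). With the SD unchanged, going from n to n − 1 participants changes the standard error of a mean by √(n/(n − 1)) − 1. For example, √(10/9) − 1 = 5.4% and √(8/7) − 1 = 6.9%. The documents give no rate of missed or unusable Day 1 draws, so q = 2%, 5% and 10% are assumptions. Expected losses are nq. If misses are independent, the chance of at least one is 1 − (1 − q)^n.

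| Arm | n | One participant | SE change, one loss | Expected losses at 2% / 5% / 10% | Chance of at least one at 2% / 5% / 10% |
|---|---|---|---|---|---|
| LN 120 mg | 10 | 10.0% | +5.4% | 0.2 / 0.5 / 1.0 | 18% / 40% / 65% |
| IgAN 120 mg | 8 | 12.5% | +6.9% | 0.16 / 0.4 / 0.8 | 15% / 34% / 57% |
| LN 180 mg | 30 | 3.3% | +1.7% | 0.6 / 1.5 / 3.0 | 45% / 79% / 96% |
| IgAN 180 mg | 24 | 4.2% | +2.2% | 0.48 / 1.2 / 2.4 | 38% / 71% / 92% |

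At a common rate q, the expected share lost is nq/n = q in every arm. The matching standard error increase is about 1/√(1 − q) − 1, which is 1.0%, 2.6% and 5.4% at 2%, 5% and 10%, whatever the arm size.

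**The case against.** The other side has several good points.

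- **The data are not discarded.** A reader might infer that one missed draw throws away all of a participant's valid concentrations. SAP 4.6.2 does not support that: concentration listings and individual figures use the Safety Set, which has no baseline condition. This point stands and limits the concern to summary tables, mean figures and parameter listings.
- **Dose selection is not shown to depend on this set.** Protocol 4.3 rests the optimal dose on PK/PD modelling, safety and efficacy. Protocol 9.4.8 describes the population PK model for participants on active treatment, and SAP 4.6.2.4 refers to a separate plan. None of these ties the modelling to the PK Analysis Set. This stands.
- **The 120 mg arms are not singled out.** It is tempting to say that the loss falls hardest there. At a common missed-draw rate the proportional loss is equal across arms. What remains is that each single exclusion costs a small arm more.
- **The draw may rarely be missed.** Day 1 is an in-clinic visit with dosing after the other procedures. No document gives a rate, so the frequencies above are illustrative only.
- **A zero baseline is an inference.** It follows from eligibility, timing and the BLQ rule; no passage states it. The inference is direct, and the rule would be unnecessary even if the value were not zero.
- **IgAN placebo participants who switch may escape.** SAP 4.1 and 6.1.2 give them a Week 26 re-baseline, which may count as the baseline PK value. The SAP does not say. This leaves the rule ambiguous for up to 24 participants without justifying it for the others.
- **The PD condition is more defensible.** Change from baseline is a PD endpoint and needs a baseline, and a single set gives absolute and change summaries the same participants. For that reason a change to the PD rule is offered only as an option.

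**Conclusion.** The concern holds in limited form. The baseline condition excludes participants with valid post-first-dose concentrations from the PK summary tables, mean figures and parameter listings, for want of a value expected to be BLQ and used by no other planned PK summary. Each exclusion takes 11 or 15 scheduled concentrations (LN) or 12 or 16 (IgAN) out of those outputs through Week 50. It costs 10% of the LN 120 mg arm or 12.5% of the IgAN 120 mg arm.

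The primary endpoint, its hypothesis test and the error rate are unaffected, and no bias is shown. The conclusion assumes that the baseline PK value means the Day 1 predose sample for participants randomized to ALXN2050, and that the planned arm sizes apply. How often the exclusion would occur cannot be judged from the documents. It is a minor, worthwhile correction.

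**What to change.** In SAP Section 3 (Table 2), define the PK Analysis Set as participants with at least 1 dose of ALXN2050 and at least 1 evaluable concentration after the first ALXN2050 dose, with no baseline condition. This also settles which baseline applies to IgAN placebo participants who switch at Week 26, because none is needed. Record the change in SAP 4.8 and align Protocol 9.3 at the next amendment; it does not warrant an amendment of its own.

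Optionally, for PD, admit participants with at least 1 evaluable value after first dose, require a baseline only for the change-from-baseline summaries, and report n for each. The cost is slightly different denominators for absolute and change summaries.

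The PK change is one table row and one entry in SAP 4.8, plus a matching protocol row later. It needs no new data, and no planned PK summary depends on the present rule.
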